7.6.4. Cross-in LMT

For patients in the FAS, cross-in LMT is defined as either initiation of new non-statin LMT or an increase in statin intensity after randomization that meets at least one of the following criteria:

1. Any statin, regardless of the specific drug, started after randomization, with increased intensity if used at baseline, and continued for 90 days or more.
2. Non-statin oral prescription LMTs (Bile Acid Sequestrants, Fibrates, Niacin Derivatives, Ezetimibe, commercial Bempedoic Acid, commercial Bempedoic Acid and Ezetimibe FDCCP, as defined in Section 7.6.1) that were not used at baseline (same preferred name), started after randomization and continued for 90 days or more.
3. PCSK9i started after randomization, not used at baseline (for evolocumab), or with increased intensity if used at baseline (specifically, for alirocumab switching from 75 mg once every two weeks to 150 mg once every two weeks or 300 mg once every 4 weeks), and continued for 90 days or more if mAb (evolocumab or alirocumab); or ≥ 1 dose for siRNA (inclisiran) after randomization, and before the EOS visit.

Since change of dosing regimen will result in a new entry on the medication CRFs, to determine the treatment duration, entries for medications of the same class (any statin, either of the PCSK9i mAbs), or the same preferred name (non-statin oral LMT) will be combined if the gaps between entries are ≤ 7 days (for oral drugs), or ≤ 30 days (for PCSK9 mAb injections).

The date of starting first adjunctive cross-in LMT is defined to be the start date of the first medication that meets the cross-in criteria.

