15.4.3. Adjunctive Cross-in Lipid-Modifying Therapy

Post randomization, LDL-C results will be masked for investigators and study participants in order to maintain the blind. Beginning at Month 6 (Visit T4) and for the remaining duration of the study, the central laboratory will notify the investigator if the patient's LDL-C level is $\geq 25\%$ higher than baseline LDL-C. The patients will be counseled on healthy dietary guidelines and reminded to take all lipid-regulating medications. The patient will return to the clinic for a repeat fasting blood lipid sample to confirm that the LDL-C value meets the threshold criteria. If confirmed, the patient's LDL-C-lowering treatment regimen may be adjusted, if possible, per standard of care and local practice. Any initiation and/or dose change of LDL-C-lowering medications will be documented on the electronic case report form (eCRF) and will not be provided by the Sponsor.

The use of adjunctive cross-in LMTs may obscure the difference between the treatment groups. To evaluate the treatment effects without cross-in LMTs, a sensitivity analysis will be performed for MACE-4 (primary) and MACE-3 endpoints in the PPS prior to cross-in LMT. Specifically, the patients are censored at the earlier of the date of starting the first cross-in adjunctive LMT therapy + 30 days and date of censoring for non-fatal events defined in Section 7.2.4, if there is no MACE-4 or MACE-3 event prior to that date.

For LDL-C and hs-CRP, observed values in changes and percent changes from baseline to Month 6 will be summarized by treatment group in the PPS, after excluding values measured after 7 days post the date of starting the first cross-in adjunctive LMT therapy.

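### SAP 7.6.4 and 15.4.3: most cross-in lipid therapy must last 90 days to count, but censoring is back-dated to start + 30 days, so it uses information from after the censoring date

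*SAP*

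**What the plan says.** SAP 7.6.4 sets the conditions for cross-in lipid-modifying therapy:

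- A statin must be started after randomization, "with increased intensity if used at baseline, and continued for 90 days or more".
- A non-statin oral prescription drug not used at baseline must be "started after randomization and continued for 90 days or more".
- A PCSK9 antibody carries the same 90-day condition. Inclisiran does not: the requirement is "≥ 1 dose for siRNA (inclisiran) after randomization, and before the EOS visit".

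The date attached to the cross-in is the start of the drug, not the day on which the 90 days are reached: "The date of starting first adjunctive cross-in LMT is defined to be the start date of the first medication that meets the cross-in criteria".

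SAP 15.4.3 uses that date in two ways. First, "a sensitivity analysis will be performed for MACE-4 (primary) and MACE-3 endpoints in the PPS prior to cross-in LMT". In it, "the patients are censored at the earlier of the date of starting the first cross-in adjunctive LMT therapy + 30 days" and the usual censoring date, "if there is no MACE-4 or MACE-3 event prior to that date". Second, observed LDL-C and hs-CRP changes to Month 6 are summarized in the PPS "after excluding values measured after 7 days post the date of starting the first cross-in adjunctive LMT therapy". In addition, SAP 13.3 summarizes time to first cross-in in the FAS.

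**The concern.** A censoring rule should use only what is known by the censoring date. Here, whether a patient is censored 30 days after starting a drug is settled by survival and drug use up to day 90. A patient who dies on the drug between days 31 and 90 cannot complete 90 days, is not a cross-in, and contributes the death. A patient with a non-fatal event in the same window who stays on the drug is a cross-in, is censored at day 30, and the event disappears. The components of the composite are thus filtered differently, in an analysis meant to show the treatment effect free of added lipid therapy.

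The arms need not be affected equally. From Month 6, a confirmed LDL-C at least 25% above baseline allows the background regimen to be adjusted (Protocol 12.1.6.3.3), so starts may be more frequent on placebo. The 90-day condition also shuts out oral and antibody starts late in a patient's follow-up, which affects the Section 13.3 summary.

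**Working it through.** **1. The rule applied to a patient who starts an oral drug or PCSK9 antibody on day 0**

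| First MACE event | Drug use afterwards | Cross-in? | Event |
|---|---|---|---|
| Any, days 0-30 | Any | Either | Kept |
| CV death, day 60 | Ends at death | No | Kept |
| Non-fatal MI, day 60 | Continues past day 90 | Yes, dated day 0 | Dropped (censored day 30) |
| Non-fatal MI, day 60 | Stopped day 70 | No | Kept |
| Any, after day 90 | Reached day 90 | Yes | Dropped |

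The third row is the ordinary course after a non-fatal event, since Protocol 10.6 expects patients to go on with study drug and visits. One case is not addressed: SAP Appendix 4 imputes partial stop dates to the month end or 31 December, which could carry a drug past a death.

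**2. Late starts.** Appendix 4 gives an ongoing drug with no stop date the end-of-study date. An oral or antibody start within 90 days of that date therefore cannot qualify. If starts were uniform from Month 6 to Month 42 (assumed), the share missed is 3/36 = 8%.

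**3. Number of events in the window, by hand.** The documents give no cross-in rate. Assume 500-1,500 starters and 3-4% per year (the design placebo rate is 3.59%):

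- Low: 500 × 60/365 × 0.03 = 2.5 events on days 31-90.
- High: 1,500 × 60/365 × 0.04 = 9.9 events.
- With an assumed fatal share of 15-20%: 0.15 × 2.5 = 0.4 to 0.20 × 9.9 = 2.0 fatal events kept. Most of the others are dropped.

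**4. Design figure.** The plan states no figure for the cross-in rule. Its event target does reproduce: for hazard ratio 0.85, two-sided alpha 0.05 and 90% power, Schoenfeld's formula gives 4 × (1.960 + 1.282)² / (ln 0.85)² = 1,592 events and Freedman's gives 1,599, against 1,620 in SAP 8.1. Power at 1,620 events is 0.905.

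**5. Effect on the hazard ratio, by simulation.**

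- From the documents: 7,000 per arm, 3.59% per year on placebo, mean follow-up 42 months, starts possible from Month 6.
- Assumed: cross-in in 10-33% of placebo and 5-19% of active patients; fatal share of first MACE-4 15-30%; 20% stop the drug before day 90; event hazard unchanged or tripled in the 90 days after a start.
- Method: 2,000,000 patients per arm, scaled to 7,000; hazard ratio taken as the ratio of events per person-time. Loss to follow-up and the PPS exclusions were not modelled.

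These shares mean 0.10 × 7,000 + 0.05 × 7,000 = 1,050 to 0.33 × 7,000 + 0.19 × 7,000 = 3,640 cross-in patients, more than in step 3.

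On days 31-90 all fatal events were kept and about 79% of non-fatal events were dropped (for example, 9.2 dropped and 2.4 kept: 9.2/11.6 = 0.79). At hazard ratio 0.85:

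| Days 31-90 | Placebo | Active |
|---|---|---|
| Fatal kept, hazard unchanged | 0.7-5.0 | 0.3-2.3 |
| Non-fatal dropped, hazard unchanged | 2.7-11.4 | 1.2-5.5 |
| Fatal kept, hazard tripled | 2.4-14.7 | 1.0-7.4 |
| Non-fatal dropped, hazard tripled | 8.5-32.6 | 3.7-16.5 |

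With hazard unchanged, the analysis counts about 1,360-1,500 events in all. The SAP rule was compared with two rules that do not look ahead: censoring at start + 30 days for every start (start rule), and censoring on the day 90 days are completed (completion rule).

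| Hazard ratio under the SAP rule, true value 0.85 | vs start rule | vs completion rule |
|---|---|---|
| Hazard unchanged | 0.0002-0.0019 lower | 0.0001-0.0021 lower |
| Hazard tripled | 0.002-0.009 lower | 0.003-0.009 higher |

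With a true hazard ratio of 1.0, the largest gap was about 0.004 with hazard unchanged and 0.011 with hazard tripled.

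**The case against.** The best defence is that the SAP means cross-in to be sustained use, so leaving out short courses is intended, and that little depends on the rule. Short or late starts can be seen elsewhere: Section 13.3 also tabulates shifts in statin intensity, Section 13.1 summarizes concomitant medication with no duration condition, and Protocol 15.9 counts patients needing added lipid therapy by class. The PPS exclusions are not legible in the public SAP, so some starters may already be out. Counting every start has its own cost: in a statin-intolerant population, brief failed retrials are foreseeable and would censor patients after minimal exposure.

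Most of this stands, and it rules out several stronger readings:

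- A reader might infer that fatal and non-fatal events are treated differently from the first day of the drug. They are not: every event in the first 30 days is kept, and inclisiran is outside the 90-day rule.
- A reader might infer that all non-fatal events on days 31-90 are lost. Those in patients who stop before day 90 are kept.
- A reader might infer a bias of known sign. The simulation shows none: with tripled hazard the SAP result lies below one comparator and above the other.
- A reader might infer that the primary result is exposed. It is not: that analysis uses the FAS without cross-in censoring, and the hierarchy in SAP 8.3 is untouched.

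The objection does not remove the look-ahead. Wanting persistence justifies the 90-day criterion; it does not justify censoring 60 days before the criterion can be known to be met. Nor is the loss of late starts part of a persistence definition: those patients may well have persisted.

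**Conclusion.** The point holds as a limited fault in a stated rule. Censoring depends on later survival and drug use, and on days 31-90 it treats fatal and non-fatal events differently. It reaches the PPS pre-cross-in analyses of MACE-4 and MACE-3, the Month 6 LDL-C and hs-CRP summaries in the PPS, and the time-to-first-cross-in summary. The hazard ratio shift is about 0.01 or less (largest simulated value 0.011) and is unlikely to change a conclusion. That size rests on assumed rates of cross-in, early stopping, fatal share and post-start hazard, none of which the documents supply. The 8% figure for missed late starts rests on uniform start times.

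**What to change.** Keep the 90-day criterion in SAP 7.6.4. In SAP 15.4.3, censor MACE-4 and MACE-3 on the day 90 days of use are completed (start + 90 days), and keep every earlier event, fatal or not. Inclisiran can stay at first dose + 30 days. If a patient has more than one qualifying drug, use the earliest resulting date. Status at any time then depends only on the past.

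The cost is a wording change and one re-derived date. The downside is 90 − 30 = up to 60 more days of adjunctive therapy in the analysis. An initiation-only version (start + 30 days whatever the later duration) can be run alongside; its weakness is that brief failed retrials count as cross-in. In Section 13.3, note that oral and antibody starts within 90 days of a patient's end of study cannot qualify.

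The same sentence of 15.4.3 points to Section 7.2.4 (visit windows) for the usual censoring date, which is defined in Section 7.2.5; correct this in the same edit.

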8. STATISTICAL CONSIDERATIONS

8.1. Sample Size

This event-driven study is designed to provide at least 90% power to detect an approximate 15% relative risk reduction in hazard ratio corresponding to the primary composite MACE endpoint (CV death, nonfatal MI, nonfatal stroke, or coronary revascularization) at an overall study significance level (alpha) of 0.05. There are no interim efficacy analyses.

A statistical relationship between on-treatment LDL-C differences between the bempedoic acid group and the placebo group and CV event risk reduction is used to derive the postulated treatment effect of 15% stated above. Assuming a 3.59% annual event rate in the placebo group, a minimum of 1620 primary composite MACE events are needed.

The average follow up duration for all patients is estimated to be approximately 42 months (~3.5 years), with an enrollment phase of approximately 33 months, a minimum follow up duration of 24 months (2 years), and a lost-to-follow-up (LTFU) rate of 1% per year. Based on these assumptions, approximately 14,000 patients (approximately 7000 in the bempedoic acid group and 7000 in the placebo group) were randomized into the study to achieve 1620 patients experiencing an adjudicated primary endpoint event.

It is expected that at least 50% of the 1620 patients experiencing an adjudicated primary 4 component MACE (810 patients) will experience an adjudicated 3 component MACE (CV death, nonfatal MI, or nonfatal stroke). Therefore, the study will not stop until at least 1620 patients have experienced an adjudicated primary MACE endpoint, with 810 patients experiencing an adjudicated 3 component MACE, and a minimum of 24 months (2 years) have elapsed since the last patient was randomized.

8.2. Multicenter Studies

This study is conducted by multiple investigators at approximately 1200 centers in 32 countries. Region (Section 7.5.1) based on the country locations of the sites is used as a covariate and for subgroup analysis. Otherwise, the study center is not considered in the analysis.

8.3. Multiplicity

There are one primary and six key secondary efficacy endpoints of interest for statistical testing in this study. A gatekeeping or hierarchical approach is used to test the primary efficacy endpoint and then key secondary efficacy endpoints sequentially to preserve the study-wise Type I error rate at 5%. For each endpoint, the null hypothesis is that of no difference between bempedoic acid and placebo groups, and the order for the hierarchical testing is:

1. time to first occurrence of MACE (CV death, nonfatal MI, nonfatal stroke, or coronary revascularization; primary 4-component MACE)
2. time to first occurrence of the composite endpoint of CV death, nonfatal MI, or nonfatal stroke (3 component MACE)
3. time to first occurrence of fatal or nonfatal MI
4. time to first occurrence of coronary revascularization

5. time to first occurrence of fatal or nonfatal stroke
6. time to CV death
7. time to all-cause mortality

For the final analysis of the differences between bempedoic acid and placebo, each hypothesis in this hierarchical order will be tested at a two-sided significance level of 0.05. Statistical significance at each step is required in order to test the next hypothesis. If any of the endpoints does not reach statistical significance, p-values for subsequent endpoints will be reported for information only.

For other efficacy and safety endpoints, a nominal p-value may be reported for information only.

8.4. Coding Dictionaries

Adverse events, medical history and procedures are coded using Medical Dictionary for Regulatory Activities (MedDRA) Version 23.1 (September 2020) including system organ class (SOC), high level term (HLT) and preferred term (PT).

Prior and concomitant medications are coded using WHO Drug Dictionary (WHO-DD) version WHODrug-DDE-B2 201809 ENG (September 2018).

8.5. Missing Data Handling

For the primary analysis of the primary and key secondary endpoints, there is no imputation. All clinical endpoints, including the types and dates of events, are adjudicated by the Clinical Event Committee (CEC) with no missing types or dates. Time-to-event analyses are carried out based on the censoring rules outlined in Section 7.2.5.

For other analyses involving missing data, specific analysis methods or imputation rules are specified in the relevant sections as needed. If not specified, general rules specified in this section apply.

8.5.1. Imputation of Missing Dates

For adverse events, and for prior and concomitant medications, if the start or end dates are incomplete, the date will appear as-is (partial or missing) in the listings. When full date is needed, e.g., to compute the Study Day, imputation rules specified in Appendix 4 will be used unless otherwise specified. In essence, AEs of uncertain start date will be considered as having started after the first dose. Medications of uncertain start or end dates will be considered as having started before, or continued after the first dose, respectively.

For LMTs (Section 7.6) and antidiabetic medications (Section 7.4.2), it is important to determine whether they were being used at baseline (i.e., the time of randomization, Section 7.6.3).

- When the medication start date is partially missing, it is imputed using the default rule. If the impute start date is before the date of randomization, and the end date is either completely missing with ongoing status of no, or only contains a year that is the same as the date of randomization, the end date is imputed with the later of the medication start date and the date of informed consent. Otherwise the default rule is used to impute the end date.

- When the medication start date is completely missing, and if the end date is either completely missing with ongoing status of no, or only contains a year that is the same as the date of randomization, both start and end dates are imputed with the date of informed consent.
- Otherwise, the start/end dates are inputted using the default rule.

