8.2. Prior and Concomitant Medications

Patients will be questioned about their concomitant medication use at each clinic visit.

Patients in this study may be using a wide range of concomitant medications, according to local standard of care for their medical conditions. Patients will be permitted to take any concomitant medications required except those listed in Section 8.2.1. Therapies to lower LDL-C may include nonstatin drugs and supplements such as ezetimibe, niacin, bile acid resins, fibrates, PCSK9 inhibitors, plant sterols, and plant stanols, but not red yeast rice. Statin use will be limited to the doses listed below and must be currently well tolerated. Additionally, patients may use any TG-lowering drugs and supplements.

All concomitant medication taken chronically or intermittently during the study must be recorded with indication, total daily dose, and start and stop dates of administration.

The Prior/Concomitant Nonstatin Medications eCRF will be used to record nonstatin medications, herbal remedies, vitamins, other supplements, and over-the-counter medications taken within 3 months prior to screening and during the study.

The Prior and Concomitant Statin Therapy for Dyslipidemia eCRF will be used to record statin medications taken at any point in the past in order to document patient's efforts to utilize statins. In addition to statin type, dose, and frequency of use, information about start dates, stop dates, and reason for discontinuation will be collected when available.

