APPENDIX 4. IMPUTATION OF DATES

The following rules will be used to impute partial missing dates. Note that imputed dates may be used to calculate ‘study day’ but will NOT be presented in the listings.

AE start date	If only Day is missing:	If the AE start year and month are the same as that for the first dose (Day 1) date, then the AE start day will be imputed as the day of first dose date; otherwise, the AE start day will be imputed as the first day of the month.
	If both Day and Month are missing:	If AE start year is the same first dose year, then the AE start Month and Day will be imputed as the Month and Day of first dose date; otherwise, the AE start date will be imputed as 01 January.
	If Year of AE start date is missing or AE start date is complete missing:	The AE start date will be imputed as the first dose date.
AE stop date	If only Day is missing:	If only Day is missing and AE stop month and year are the same as the month and year of the EOS date, use the EOS date; otherwise the last day of the month will be imputed.
	If both Day and Month are missing:	If both Day and Month are missing and AE stop year is the same as the year of the EOS date, the EOS date will be used to impute. If the year of the AE end date precedes the year of the EOS date, AE end month and day will be set to 31 December.
	If the Year of AE stop date is missing or AE stop date is completely missing:	If the AE stop date is completely missing, 1) if the “Ongoing” status is “Yes”, the EOS Date will be assigned to the stop date; 2) if the “Ongoing” status is “No” or missing, the stop date will be assigned as the Date of Informed Consent, or the start date if present (partially imputed if necessary) and later. If only Year is missing, the EOS year will be assigned to the stop date.

AE = adverse event; EOS = End-of-Study

Medication start date	If only Day is missing:	If only Day is missing, the first day of the month will be assumed.
	If only Day and Month are missing:	If both Day and Month are missing, the first day of the year will be assumed.
	If only Year is missing or date is completely missing:	If medication start date is completely missing, the informed consent signature date or medication end date whichever is earlier, will be used to impute.

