AE start date	If only Day is missing:	If the AE start year and month are the same as that for the first dose (Day 1) date, then the AE start day will be imputed as the day of first dose date; otherwise, the AE start day will be imputed as the first day of the month.
	If both Day and Month are missing:	If AE start year is the same first dose year, then the AE start Month and Day will be imputed as the Month and Day of first dose date; otherwise, the AE start date will be imputed as 01 January.
	If Year of AE start date is missing or AE start date is complete missing:	The AE start date will be imputed as the first dose date.
		If only Year is missing, then informed consent signature year will be used to impute.
Medication stop date	If only Day is missing	If only Day is missing, the last day of the month will be assumed.
	If both Day and Month are missing	If both Day and Month are missing, the medication stop month and day will be set to 31 December.
	If Only Year is missing or medication end date is completely missing	If medication end date is completely missing, 1) if the “Ongoing” status is “Yes”, the EOS Date will be assigned to the stop date; 2) if the “Ongoing” status is “No” or missing, the end date will be assigned as the Date of Informed Consent, or the start date if present (partially imputed if necessary) and later. If only Year is missing, the EOS year will be assigned.
Other dates	If only Day is missing	If only Day is missing, the last day of the month will be assumed.
	If only Day and Month are missing:	If both Day and Month are missing, the first day of the year will be assumed.
	If the year is missing, or the date is completely missing.	Will not be imputed.

AE = adverse event; EOS = End-of-Study

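### A lipid-drug start recorded only to the year is set to 1 January without reference to randomization, so added therapy can be coded as baseline or an earlier MACE can drop out of the pre-cross-in analysis

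*SAP*

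**What the plan says.** SAP 8.5.1 singles out lipid-modifying and antidiabetic drugs because baseline use matters for them, but leaves the start date to the general rule: "When the medication start date is partially missing, it is imputed using the default rule". Appendix 4 supplies that rule. For a medication start, "If only Day is missing, the first day of the month will be assumed", and "If both Day and Month are missing, the first day of the year will be assumed". The stated direction is deliberate: "Medications of uncertain start or end dates will be considered as having started before, or continued after the first dose, respectively".

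The lipid-specific text in 8.5.1 changes only the end date when the start is partial. If the imputed start precedes randomization and the end is either missing with ongoing status no, or known only to the randomization year, the end becomes the later of the start and the consent date.

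The imputed start then drives three definitions:
- Baseline therapy (7.6.3) is anything ongoing at randomization.
- Cross-in therapy (7.6.4) must start after randomization, and "The date of starting first adjunctive cross-in LMT is defined to be the start date of the first medication that meets the cross-in criteria".
- In the pre-cross-in sensitivity analysis (15.4.3), "the patients are censored at the earlier of the date of starting the first cross-in adjunctive LMT therapy + 30 days" and the ordinary censoring date, unless a MACE came first.

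**The concern.** An early default suits old medication history, where the aim is to avoid calling a long-standing drug new. It does not suit a drug added during the trial. There, the imputed date can cross randomization and turn added therapy into background therapy, or cross a MACE and turn an observed event into a censored time.

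The second error depends on outcome: it removes events that led to treatment. The first lets a post-randomization act decide membership of a subgroup labelled baseline. The outputs exposed are:
- cross-in counts and time to first cross-in (SAP 13.3);
- the pre-cross-in MACE-4 and MACE-3 analysis (15.4.3);
- the baseline statin and ezetimibe subgroup and covariate analyses (15.5.1, 15.5.2);
- the tables restricted to baseline ezetimibe users (for example 9, 14 and 16.1.1).

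**Working it through.** The plan states no figure on this point, so there is none to reproduce. The check is date arithmetic under the SAP's rules.

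**Notation.** R = randomization, S = true start, I = imputed start, M = MACE date.
- Coded baseline if I < R and the drug is ongoing at R.
- Otherwise, if the other cross-in criteria are met, censored at I + 30 days.
- Window in which a MACE before the true start is dropped = max(0, S − (I + 30)).

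**Month-only date (day missing).** S − I is at most 30 days, so the window is 0 for every date. Coding as baseline requires S in the calendar month of R. With all calendar dates equally likely, starts 1–30 days after R are miscoded for 46% of date pairs, and starts 182 or more days after R for 0%.

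**Year-only date.** S − I is at most 364 days (365 in a leap year), with mean 182. The window is therefore at most 334 or 335 days (mean 153). It is open for any start after 31 January: (365 − 31)/365 = 91.5% of start dates. The share of date pairs coded as pre-randomization, with calendar dates equally likely, is:

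| True start, days after R | Coded before R |
|---|---|
| 1–182 | 75% |
| 182–273 | 37% |
| 182–365 | 25% |
| 366–730 | 0% |

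**Example 1, coded as baseline.** R = 15 Mar 2018, S = 10 Oct 2018 (day 209), recorded as 2018, ongoing. I = 1 Jan 2018, which precedes R. The drug is baseline therapy and not cross-in.

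**Example 2, MACE dropped.** R = 15 Jun 2018, M = 15 Aug 2020, S = 10 Oct 2020, recorded as 2020. I = 1 Jan 2020, so censoring is on 31 Jan 2020 and the MACE is lost. With the true date, censoring would be on 9 Nov 2020 and the MACE would count. With a month-only date, I = 1 Oct 2020, censoring is on 31 Oct 2020, and the MACE again counts.

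The two errors cannot arise from the same record: a start moved before R triggers no censoring.

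**Share of event-prompted, year-only starts that lose their event.** From the documents: enrolment over 33 months and 3.59% per year. Assumed: uniform enrolment, exponential events, common stop 5.2 years after first randomization, drug started 0–60 days after the event, and enrolment opening in January, April, July, October or December. Results: 69% to 73% lose the event. Another 11% to 13% start in the randomization year, are coded baseline and keep it. The remaining 15% to 18% keep it because the event precedes 31 January of the start year.

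**Number of events.** The documents do not give the share of event patients who add a lipid drug or the share of year-only dates. Assuming 30% for the first and a range for the second, on the planned 1,620 events: lost = 1,620 × 0.30 × p × 0.70. This gives about 7 (p = 2%), 17 (5%), 34 (10%) and 68 (20%). A simulation of 7,000 per arm with hazard ratio 0.85, adding assumed LDL-C-alert starts of 3% per year on placebo and 0.6% on active, gave about 6, 17, 34 and 64. The hazard ratio moved by 0.003 or less when date quality was equal by arm.

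**The case against.** The strongest reply is that the pattern should be rare and its reach is limited. Protocol 8.2 requires start and stop dates for all medication taken during the study, and Protocol 12.1.6.3.3 requires any initiation or dose change of an LDL-C-lowering drug to be documented. Medication is reviewed at every treatment visit, including the phone visits. The 8.2 wording that "information about start dates, stop dates, and reason for discontinuation will be collected when available" belongs to the paragraph on past statin use and is not evidence that in-study dates are poor. All of this stands. It bears on how often the problem arises, not on what the rule does when it arises.

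A reader might infer more than the documents support:
- That every partial date goes to the earliest possible day. Not quite: "If only Year is missing, then informed consent signature year will be used to impute".
- That any partial date can cost a MACE. A missing day alone cannot, because the 30-day allowance absorbs the whole shift.
- That about 11 in 12 event-prompted starts lose their event. That confuses the share of start dates with an open window (91.5%) with the share of events lost (about 70%).
- That the trial's main result is at risk. SAP 8.5 uses no imputation in the primary analysis of the primary and key secondary endpoints. The lost events fall in one per-protocol sensitivity analysis, and the subgroup and covariate analyses are exploratory or supportive.
- That the treatment effect is biased by arm. That would need date quality to differ between arms; recording is double-blind and nothing in the documents suggests it does.
- That background therapy is routinely turned into cross-in by the end-date rule. This needs a year-only stop in the randomization year on the old entry and a more precise start on its replacement. It is possible but narrow.

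**Conclusion.** The point holds for year-only starts. Applied as written, 8.5.1 and Appendix 4 code an ongoing lipid drug added later in the randomization year as baseline therapy. They also drop a MACE that preceded a drug started in a later year, whenever the MACE falls on or after 31 January of that year. Month-only dates cause only the first error, and only for starts in the calendar month of randomization.

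About 70% of event-prompted, year-only starts would lose their event, conditional on the drug starting within 60 days. The absolute number cannot be derived: the count of partial dates is not given, and the event figures rest on assumed inputs and the full randomized numbers, whereas the analysis uses the per-protocol set, whose exclusions are not visible. The primary analysis is untouched, and with equal date quality by arm the effect on the hazard ratio is likely very small. The case for change is that a planned sensitivity analysis loses events in an outcome-dependent way and that baseline labels can be wrong, both of which can be avoided cheaply.

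**What to change.** Before unblinding, count the lipid-drug entries with partial start dates, separating month-only from year-only. Then amend 8.5.1 for lipid drugs:

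1. Where medication-review data or entry dates show that the drug was not listed by T1, do not code it as baseline. Impute its start no earlier than the day after the last review that did not list it.
2. Where the entry was listed as in use at T1, do not impute a stop before randomization.
3. Where no such data exist, run the pre-cross-in MACE-4 and MACE-3 analysis twice, with the earliest and the latest possible start (the latter capped at the stop date), and report both.

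The cost is SAP wording and extra programming. The documents do not show that the CRF stores the visit at which a drug was first listed, so the first two rules may be usable for only some entries. The latest-date version has its own error: a year-only start moved to 31 December is about six months late on average, so some patients stay in the analysis for a time after the added therapy began. That is why both versions should be reported.
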